#### 1.4. Benefit/Risk Assessment

Although SBP-9330 has not been administered to humans previously, the potential risks to human subjects associated with SBP-9330 are detailed in the Summary of Data and Guidance for the Investigator within the Investigator's Brochure.

Considering the 40-fold safety factor based on the 2-week NOAEL values of rat and dog and the projected starting human therapeutic dose range of SBP-9330 of 300-600 mg/day, the proposed starting dose of 150 mg/day is not expected to induce any potential risk or benefit to subjects participating in this study.

In addition to specific safety stopping criteria (Section 3.5), dose-escalation PK stopping criteria will be implemented such that systemic exposures in subjects do not exceed  $1/10^{th}$  of the AUC0-24hr and Cmax levels associated with the identified NOAEL of the GLP 14-day rat study.

Routine clinical assessments including hematology, chemistry, and urinalysis will be performed as a means of monitoring subject safety. Potential safety considerations were limited to minor clinical pathology alterations in glucose, albumin, total protein, triglycerides and cholesterol (total and HDL) based on nonclinical safety assessments. As such, subjects will be monitored for adverse effects related to these parameters.

Overall, the safety monitoring practices employed by this protocol (i.e., physical examination, 12-lead electrocardiogram (ECG), vital signs (including orthostatic blood pressures and pulse

<sup>1animal NOAEL in mg/kg × 0.16 (rat), 0.54 (dog)

<sup>2HED × 60 kg human subject ÷ Safety Factor of 10

Altasciences Project Number: CNO-P5-319

rate), clinical laboratory tests, Columbia-Suicide Severity Rating Scale (C-SSRS) questionnaire, and AEs) are adequate to protect the subjects' safety and should detect all expected treatment-emergent AEs (TEAEs).

There will be no direct health benefit for study participants from receipt of the study drug. An indirect health benefit to the healthy subjects enrolled in this trial is the free medical tests received at Screening and during the study.

Altasciences Project Number: CNO-P5-319

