## 3. STUDY DESIGN

## 3.1. Adaptive Features and Risk Management of Study Design

The rationale for the following adaptive features is based on taking an iterative, hypothesis-forming approach in this clinical trial. The following categories will be adapted as shown in Table 6.

**Table 6** Adaptive Features and Boundaries

Adaptive study design category	Adaptive Features	Boundaries
Dose level for the SAD cohorts	SAD dose levels may be adjusted based on safety and available PK data reported in the previous cohort(s).	Doses are intended to escalate; however, they may be adjusted to an intermediate (lower) or equivalent dose, based on safety and available PK data reported in the previous cohort(s).  Escalation from one dose level to the next dose level will not be more than 3-fold the previous dose.
Dose level for the MAD cohorts	Doses for the MAD cohorts will be adapted in accordance with safety and available PK data collected in previous cohorts during the SAD or MAD phase.	The first MAD dose must be lower or equal to a dose administered in a SAD cohort for which safety and PK data are available.  Doses are intended to escalate; however, they may be adjusted to an intermediate (lower) or equivalent dose, based on safety and available PK data reported in the previous cohort(s).  Escalation from one dose level to the next dose level will not be more than three-fold the previous dose.  A MAD daily dose level cannot be higher than the highest dose level tested in SAD.
Dose level for the Smoker cohorts	Smoker cohort dose levels will be adapted in accordance with safety and available PK data collected in previous cohorts during the SAD or MAD phase.	The first Smoker dose must be lower or equal to a dose administered in a MAD cohort for which safety and PK data are available.  Doses are intended to escalate; however, they may be adjusted to an intermediate (lower) or equivalent dose, based on safety and available PK data reported in the previous cohort(s).  Escalation from one dose level to the next dose level will not be more than three-fold the previous dose.  A Smoker cohort daily dose level cannot be higher than the highest dose level tested in the MAD phase.
Dosing frequency for the MAD and Smoker cohorts	The dosing frequency may be modified from once daily to twice daily.	The modification from once daily to twice daily administration will not change the total daily dose outlined in this protocol.

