The quantity of cohorts in each phase (SAD or MAD)	The quantity of cohorts may be decreased.	The maximum number of cohorts for the SAD and MAD phase are 5 and 4, respectively.  The number of cohorts in each phase may be decreased at the discretion of the Sponsor

Altasciences Project Number: CNO-P5-319

Adaptive study design category	Adaptive Features	Boundaries
		depending on the emerging safety and PK data from the previous cohorts.
The quantity of cohorts during the Smoker phase	A 3 rd cohort may be added.	The Smoker phase will have a maximum of 3 cohorts. There are 2 planned cohorts and an additional cohort may be added depending on the emerging PK and safety data in the previous cohorts.
Overlap between SAD and MAD phases	The MAD phase of the study may commence in parallel to the SAD or thereafter.	The decision on how early the MAD phase of the study may start and the doses to be administered will be determined by the Sponsor after consultation with the DSMB based on emerging safety and PK data.  A MAD dose level cannot be higher than the last dose level administered in the SAD phase.
Blood collection during the MAD phase	The PK blood sampling timepoints during the MAD phase may be modified.	Depending on data obtained during the SAD phase, the PK sampling timepoints during the MAD phase may be modified in order to optimize characterization of PK parameters of interest.
Food-Effect cohort	The food-effect cohort may be done in a cohort with a dose level other than 600 mg.	Depending on data obtained in the previous cohorts, the food-effect may be evaluated at a dose level other than 600 mg to optimize characterization of PK parameters of interest.

Abbreviations: DSMB = Data and Safety Monitoring Board; MAD = multiple ascending dose;

PK = pharmacokinetic; SAD = single ascending dose

The decision-making process for the above adaptive study categories will be as follows, unless otherwise stated:

- Interim review of safety and emerging PK data for SBP-9330 from completed or ongoing SAD, MAD, or Smoker cohorts in a blinded fashion by the Data and Safety Monitoring Board (DSMB). For Part C (Smoker Phase), the DSMB will be provided the randomization code to aide in the review of safety and PK data.
- Outcome on the adaptive study category will be documented by the DSMB.

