#### 3.2. Data and Safety Monitoring Board (DSMB)

A DSMB will be established to assure that the safety of the study subjects is protected while the scientific goals of the study are being met. Specifically, the DSMB is charged with monitoring the safety of participants and the quality of the data, as well as the appropriate termination of studies when risks have been uncovered or when it appears that the clinical trial cannot be

Altasciences Project Number: CNO-P5-319

concluded successfully. The DSMB is responsible for reviewing and evaluating safety and available plasma PK data collected after each cohort.

The DSMB will be comprised of voting members who are independent of the Sponsor and CRU and will, at a minimum, include physicians experienced in drug safety. The composition and operations of the DSMB will be detailed in a separate document that will serve as the Data and Safety Monitoring Plan (DSMP).

The DSMB will review safety data up to discharge and available plasma PK data of all the subjects in the respective cohort in a blinded manner to provide recommendations to the Sponsor and PI whether to escalate doses between cohorts. The minimum number of subjects required to decide on dose escalation is six subjects (i.e., at least four on active treatment) for Part A (SAD) and eight subjects (i.e., at least six on active treatment) for Parts B (MAD) and C (Smoker).

The DSMB will also advise as to when MAD dosing may commence and whether any stopping criteria were met. For Part A and Part B, these assessments will generally be made without breaking the blinded randomization code. For Part C, the DSMB will be provided the randomization code to aide in the review. If judged necessary by the DSMB, an individual or the complete cohort may be unblinded during evaluation of the study data. Before unblinding, a decision should be made about the action to be taken based on the revealed treatment allocation. The DSMB may adjust the dose based on the treatment-emergent safety and available PK data.

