### 3.3.2. Part B - MAD Phase

Screening of participants will occur within approximately 28 days prior to the first scheduled administration of study medication. Screening data will be reviewed to determine subject eligibility. Subjects who meet all inclusion criteria and none of the exclusion criteria and who consent to participation will be admitted to the CRU for baseline evaluations before dosing (Day -1). All baseline safety evaluation results should be available prior to dosing and continued eligibility confirmed.

Subjects will be randomized to SBP-9330 or placebo in 1 of the 3 ascending dose cohorts (10 subjects per cohort in 4:1 [SBP-9330:placebo] ratio) to have a total of 8 subjects receiving SBP-9330 and 2 subjects receiving placebo. An additional MAD cohort (Cohort B4) may be

Altasciences Project Number: CNO-P5-319

added at the discretion of the Sponsor depending on emerging safety and PK data from previous cohorts.

The proposed MAD design and planned escalation are presented in Table 8.

Table 8 Part B - MAD Phase Design and Dose Levels

Cohort	N (active:placebo)	Dose	Drug administrations
B1	8:2	adaptive	Once daily oral administrations of SBP-9330 or placebo for 14 consecutive days (Days 1 to 14) under fasting conditions
B2	8:2	adaptive	Once daily oral administrations of SBP-9330 or placebo for 14 consecutive days (Days 1 to 14) under fasting conditions
В3	8:2	adaptive	Once daily oral administrations of SBP-9330 or placebo for 14 consecutive days (Days 1 to 14) under fasting conditions
Additional B4	8:2	adaptive	Once daily oral administrations of SBP-9330 or placebo for 14 consecutive days (Days 1 to 14) under fasting conditions

Each subject will receive once daily oral administration of the assigned treatment and dose under fasting conditions (SBP-9330 or placebo) for 14 consecutive days.

The MAD phase of the study may commence in parallel to the SAD or thereafter. The decision on how early the MAD phase of the study may be started and the doses to be administered will be determined by the Sponsor after consultation with the DSMB based on emerging safety and PK data. The first MAD daily dose will be less than or equal to an already well-tolerated SAD dose for which complete safety and PK data are available.

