# 3.5. Dose Escalation and Stopping Rules

Escalation to the next higher dose will only proceed if none of the stopping criteria below have been reached and when the safety and tolerability and plasma PK analysis of the previous dose, including delayed emergence of significant AEs in earlier cohorts, are acceptable to the Investigator, Sponsor and DSMB. Dose escalation will be stopped if it is determined that the limits of safety and/or tolerability or the PK stopping criteria (Section 3.5.2) have been reached. This decision will be made by the Sponsor and the Principal Investigator based on DSMB recommendation. If dose escalation is stopped due to any findings, additional cohorts may receive the same or lower doses of the investigational compound. However, in the event that the findings are likely related to  $C_{max}$ , dose escalation may continue by dividing the dose ensuring that the  $C_{max}$  is the same or lower.

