## 3.5.2. Cohort Stopping Rules

If any of the following safety concerns are observed, dosing of all subjects at the given dose level or higher will be suspended/halted and all available data will be evaluated by the DSMB.

Dose continuation (remaining subjects within a cohort or remaining dosing for a subject) or escalation should not proceed for any of, but not limited to, the following reasons:

- If one SBP-9330-related SAE occurs in a cohort
- Severe AE at least possibly related to SBP-9330 in two or more subjects in the same cohort\*
- Other findings that, at the discretion of the DSMB or Sponsor, indicate further dosing should be stopped

\* Prior to suspending the cohort, if severe AEs are reported in two or more subjects at a given dose level, consideration should be given to the treatment assignment (SBP-9330 or placebo). After causality assessment, the Investigator (or designee) should open the individual randomization code to verify the treatment received. Dosing at the given dose level may continue if only one subject received SBP-9330 and the other(s) received the placebo.

Subjects experiencing severe AEs will be followed up with serial measurements of the related clinical parameter(s), as per medical judgment, until resolution, stabilization, or until the subject is lost to follow-up.

Dose escalation will be discussed during the DSMB meeting and may be stopped depending on Principal Investigator's or Sponsor's decision, based on but not limited to the following:

- New clinically significant abnormalities in physical examination, 12-lead ECG, or vital signs in two or more subjects
- Overall pattern of clinical changes or symptoms that may have appeared minor in terms of an individual AE or subject, but which collectively present a safety concern
- Clinically significant changes in organ-specific laboratory parameters (e.g., liver function enzymes in one or more subjects)
- Pattern of laboratory changes (e.g., a consistent increase or decrease in two or more subjects or within or across dosing cohorts) that might indicate an overall safety concern

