In addition to the safety stopping criteria listed above, dose-escalation PK stopping criteria will be implemented such that systemic exposures in subjects do not exceed  $1/10^{th}$  of the  $AUC_{0-24hr}$  and  $C_{max}$  levels associated with the identified NOAEL of the GLP 14-day rat study. The  $1/10^{th}$  stopping values for  $C_{max}$  and  $AUC_{0-24hr}$  are 25.4  $\mu g/mL$  and 224  $\mu g^*$  hr/mL, respectively. Dose escalation in the SAD, MAD, or Smoker components of the study will be stopped before these exposures are achieved.

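### The first MAD dose is capped by a SAD dose level, not by projected steady-state exposure, so the plan permits (but does not make likely) a B1 dose that meets the PK limits once and exceeds them on repeat dosing

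*Protocol*

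**What the plan says.** Protocol section 1.4 states the aim: "dose-escalation PK stopping criteria will be implemented such that systemic exposures in subjects do not exceed" one-tenth of the AUC0-24 and Cmax at the NOAEL of the 14-day GLP rat study. Section 3.5.2 gives the values, Cmax 25.4 ug/mL and AUC0-24 224 ug*hr/mL, and adds: "Dose escalation in the SAD, MAD, or Smoker components of the study will be stopped before these exposures are achieved". Section 3.5 attaches the same action, with the criteria having been reached as the trigger: "Dose escalation will be stopped if it is determined that the limits of safety and/or tolerability or the PK stopping criteria".

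The dose of B1 is bounded separately. The MAD row of Table 6 (section 3.1) says "The first MAD dose must be lower or equal to a dose administered in a SAD cohort", provided safety and PK data are available for that dose. Section 3.3.2 says "The first MAD daily dose will be less than or equal to an already well-tolerated SAD dose", and there the safety and PK data must be complete. Neither bound contains an exposure or accumulation term.

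Other provisions bear on B1. Under section 3.3.2 the Sponsor sets the MAD doses after consulting the DSMB on emerging safety and PK data. Under section 3.2, "The DSMB will also advise as to when MAD dosing may commence and whether any stopping criteria were met". Section 3.1 provides for blinded DSMB review of safety data and of "emerging PK data for SBP-9330 from completed or ongoing SAD, MAD, or Smoker cohorts". SAP section 10 produces preliminary PK results, including Cmax and AUCs, after each SAD and MAD cohort and before the next escalation. Neither document requires a projection of steady-state exposure before B1.

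**The concern.** The exposure limit and the dose cap for B1 do not measure the same thing. The AUC limit is derived from a rat exposure after 14 daily doses. A SAD cohort is checked against it with the AUC0-24 of one dose. B1 may then receive that same dose every day for 14 days. If the drug accumulates, a dose that was inside the limit in Part A can be outside it in Part B.

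The stop on escalation does not clearly catch this, because B1 at or below a SAD dose already given need not be an escalation. Table 6 carries weight here: section 3.1 lets the next dose cohort proceed without prior IRB or regulatory approval as long as the adaptation stays inside the stated boundaries. What is at stake is whether those boundaries deliver the protection that section 1.4 describes.

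**Working it through.** **Inputs.** Rat AUC on Day 14 at the NOAEL of 600 mg/kg/day: 635,000 (males) and 2,240,000 (females) hr*ng/mL (section 1.2.2). Limits: 224 ug*hr/mL and 25.4 ug/mL (section 3.5.2). Dosing interval: 24 h. Human half-life: not given, so 6 to 48 h is assumed.

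**The plan's own figure.** 2,240,000 / 10 / 1000 = 224 ug*hr/mL. The AUC limit is therefore one-tenth of the female Day 14 value, a repeat-dose exposure. The Cmax limit implies a rat Cmax of 254 ug/mL, which is not printed for the GLP study and cannot be checked.

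**Accumulation.** Under linear one-compartment PK with rapid absorption, single-dose AUC0-24 is the fraction f = 1 - 2^(-24/half-life) of AUC0-inf, and steady-state AUC0-24 equals single-dose AUC0-inf. The accumulation ratio is 1/f. A single-dose AUC0-24 above 224 x f, while still below 224, meets the limit once and exceeds it at steady state. The same factor applies to Cmax.

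| Assumed half-life (h) | f | Ratio 1/f | AUC threshold 224f | Cmax threshold 25.4f |
|---|---|---|---|---|
| 6 | 0.9375 | 1.07 | 210 | 23.8 |
| 12 | 0.75 | 1.33 | 168 | 19.1 |
| 24 | 0.50 | 2.00 | 112 | 12.7 |
| 48 | 0.293 | 3.41 | 66 | 7.4 |

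With a 2 h absorption half-life instead, the AUC thresholds fall to about 203, 157, 102 and 59, and the Cmax thresholds to 23.1, 18.0, 11.9 and 7.1.

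**How soon the limit would be passed.** Day n AUC0-24 = (single-dose AUC0-24 / f) x (1 - 2^(-24n/half-life)).
- 180 at 12 h: 180/0.75 x 0.9375 = 225 on Day 2.
- 150 at 24 h: 150/0.50 x 0.75 = 225 on Day 2.
- 100 at 48 h: 221 on Day 3 and 256 on Day 4.

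**What the default schedule would show.** Under section 6.3, the next sample after the Day 1 24 h draw is the Day 7 predose trough, and the only repeat-dose profile is on Day 14. The share of steady state reached after six doses is 1 - 2^(-144/half-life): 0.9998, 0.984 and 0.875 at 12, 24 and 48 h. On that default, review within B1 would come after most of the accumulation.

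**Whether SAD data can supply the projection.** AUC0-inf and half-life are planned Part A parameters (Table 15; SAP Table 7), but they are set to Not Reported when extrapolated area exceeds 20% (section 8.4.5). With sampling to 48 h, that area is 2^(-48/half-life): 6%, 25% and 50% at 12, 24 and 48 h. It passes 20% at 48/log2(5) = 20.7 h, where the accumulation ratio is already 1.81. The preferred input can therefore be missing where accumulation is larger.

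**The case against.** The strongest reply is that the design already makes a B1 dose near the limit unlikely. MAD doses are intended to ascend over three planned cohorts, none may exceed the highest SAD dose, and SAD escalation is to stop before the limits are reached. Suppose the MAD steps are 2-fold, as the SAD steps are, and B3 is no higher than the top SAD dose. Then B1 is at most a quarter of that dose: single-dose AUC0-24 at most 224/4 = 56 and Cmax at most 25.4/4 = 6.35. Both lie below every threshold above, including those with slow absorption. With 1.5-fold steps, B1 is at most 224/2.25, about 100, and the AUC limit is passed only above a half-life of roughly 28 h (rapid absorption). This stands as an argument about likelihood. It is not a guarantee, because MAD step size is not fixed, and Table 6 allows equal or lower doses after B1 and fewer cohorts.

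Three further points stand. Under linear PK, SAD AUC0-inf is itself the steady-state AUC projection, so the data and the decision point exist and only a written comparison is missing. Table 6 lets MAD sampling times be changed on SAD data, so the gap from Day 1 to Day 7 is a default. Dosing can also be halted under section 3.5.2 for "Other findings that, at the discretion of the DSMB or Sponsor, indicate further dosing should be stopped". A rule may exist in the separate Data and Safety Monitoring Plan, which is not available here.

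A reader might go further and infer that B1 would be chosen without human PK, or that the DSMB can look only at observed exposure. The documents support neither. Section 3.3.2 requires complete SAD PK first, and nothing prevents the Sponsor or the DSMB from making the projection.

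**Conclusion.** The point holds as a gap in a written boundary. The cap on B1 is a dose level, the exposure limits act only through a stop on escalation, and no projection is required. A dose that satisfies the cap can therefore break the limit that section 1.4 says will not be exceeded. Discretion could prevent this, but the stated rule does not.

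The size is conditional. At a half-life of 6 h, only SAD exposures within about 6% of the AUC limit are affected; at 24 h, the upper half of the allowed range is. These figures assume linear one-compartment PK and a half-life that the documents do not give, and they describe SAD exposures, not expected B1 doses. Whether any planned dose reaches these exposures is unknown, so the documents do not support reading this as a prediction that B1 will exceed the limits. Escalation between MAD cohorts and within Part C is not in question, because the PK criteria expressly apply there.

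**What to change.** In the MAD row of Table 6, in protocol section 3.5.2 and in SAP section 10, add a requirement that applies before B1 dosing. Steady-state AUC0-24 and Cmax at the candidate dose are projected from SAD data and must both be below the existing limits.

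- AUC: use SAD AUC0-inf, scaled to the candidate dose if needed. Where it is Not Reported, use the value based on the estimated lambda-z, for this projection only and labelled as such.
- Cmax: use superposition of the single-dose profile.
- Statistic: show the comparison for individual subjects and for the cohort geometric mean, and state which one decides. Neither document names the statistic for the existing limits.
- Consequence: if the projection reaches a limit, B1 starts at a lower dose.

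The cost is a few lines of wording and one calculation on PK already planned. The downside is a possibly lower B1 dose. Superposition also assumes that clearance does not change on repeat dosing, and the lambda-z fallback is less precise when half-life is long. In a simulation of cohorts of six active subjects on the 48 h schedule (1 h absorption half-life, assumed log-SD 0.25 in elimination rate and 0.20 in volume, 10% assay error), the cohort geometric mean of projected over true AUC0-inf had a 5th to 95th percentile range of 0.98 to 1.03 at a half-life of 12 h, 0.96 to 1.08 at 24 h, and 0.89 to 1.28 at 48 h. These ranges depend on that single set of assumed variances.
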